#### **6.2.5 Day 36 Visit, 7 (+1) days after the second study vaccination – Clinic follow-up visit**

*Only for those in Cohorts 2 or 4, who have received a second study vaccination*

At the Day 36 Visit, the participant will return to the study clinic for the following procedures:

- Review with participant the completed memory aid and ensure that the participant has correctly interpreted the instructions in completing the memory aid; any required corrections to be clearly documented
- Collect any new AEs since Day 29 Visit that have not already been captured and review any AEs that are currently ongoing
- Collect any new concomitant medications since Day 29 Visit that have not already been captured and review any concomitant medications that are currently ongoing
- If the participant reports any intervening symptom or AE since the previous visit, perform a targeted physical examination, which is to include vital signs
- Any topics or new information considered by investigator to be important to continued informed consent to be shared with the participant
- Provide participant with instructions and supplies to collect stool specimens within the appropriate windows on study Days 43, 50, and 57 prior to their next scheduled visit
- Provide participant clear guidance on appropriate hygienic measures and supplies to minimize contact and contamination during the stool collection process (e.g., collection kit, sanitizer, disinfectant, gloves) and minimize risk of transmission of vaccine virus to others
- Provide participant information about storage and transport of stool specimens to the study site
- Schedule next study visit (Day 57 Visit) and instruct participant to contact study staff for any symptoms of concern, and ensure participant has appropriate contact details for the study team

#### **6.2.6 Day 57 Visit, 28 (+2) days after the second study vaccination – Clinic follow-up visit**

*Only for those in Cohorts 2 or 4, who have received a second study vaccination*

At the Day 57 Visit, the participant will return to the study clinic for the following procedures:

- Collect any new AEs since Day 36 Visit that have not already been captured and review any AEs that are currently ongoing
- Collect any new concomitant medications since Day 36 Visit that have not already been captured and review any concomitant medications that are currently ongoing
- If the participant reports any intervening symptom or AE since the previous visit, perform a targeted physical examination, which is to include vital signs
- Any topics or new information considered by investigator to be important to continued informed consent to be shared with the participant
- Collect venous blood sample (approximately 10 mL) for neutralizing antibodies to type-specific polioviruses
- Schedule next study visit (Day 169 Visit), which will occur via telephone and instruct participant to contact study staff for any symptoms of concern and ensure participant has appropriate contact details for the study team
- If cessation of vaccine virus shedding has not been confirmed by Day 57 stool sample, ask participant to continue with stool collections and the associated protocol restrictions until informed that cessation of shedding has been confirmed. Ensure that cessation of vaccine virus shedding has been ultimately confirmed.

If poliovirus shedding is detected by PCR on one of the last two scheduled stool samples, stool sample collection duration for that participant will be extended. As soon as the shedding results are known (anticipated approximately two weeks after the last stool sample provided for evaluation) the participant will be asked to collect additional stool samples after the last per protocol sample obtained over a period no shorter than 24 hours, and to repeat this until shedding is PCR-negative for poliovirus on two consecutive stool samples collected. They will be provided additional stool collection kit for each sampling day.

If the last stool sample is missing the participant will be asked to provide a new sample as soon as possible in order to determine the need for further stool sample collection until poliovirus shedding is PCR negative on two consecutive stool samples.

#### **6.2.7 Day 169 Telephone Visit, 168 (+14) days after the initial study vaccination – Final Study Visit**

At Day 169, the participant is expected to be available for a telephone follow-up for the following procedures:

- Collect any new SAEs reported since previous Visit that have not already been captured and review SAEs that are currently ongoing
- Collect any new SAE associated concomitant medications reported since previous Visit that have not already been captured and review any SAE associated concomitant medications that are currently ongoing
- Instruct participant to come to the clinic for a targeted physical exam, including vital signs, if they report any intervening symptom or AE since the previous visit that is of clinical concern

#### **6.2.8 Unscheduled Visits**

Unscheduled visits (those between regularly scheduled follow up visits) may be performed at participant request or as deemed necessary by the investigator at any time during the study. All unscheduled contacts and visits will be documented in the participant's study records and on applicable case report forms.

### **6.3 Discontinuation of Vaccination or Study Procedures**

Participants have the right to decline study vaccinations or procedures for any reason and at any time during the study. If a participant declines further vaccination or study procedures, this will be recorded as a study deviation and the reason will be clearly documented in the source document. The participant will be encouraged to complete the remaining applicable safety related follow-ups and immunogenicity blood draw. If the participant does not wish to remain in the study by declining any follow-up or procedures, the participant can choose to withdraw consent and be withdrawn from the study.

Discontinuation from further vaccination may be at the discretion of the investigator or Protocol Safety Review Team (PSRT), if determined to be in the participant's best interest to do so (e.g., safety concern). In addition, participants will be discontinued from further vaccination for the following reasons:

- Pregnancy
- Ineligibility (either arising during the trial or retrospectively having been overlooked at screening)
- Significant or repeated non-compliance with trial requirements
- An adverse event which requires discontinuation of study vaccination or results in inability to continue to comply with trial procedures
- Intercurrent illness or diseases or medical treatment that occur during the trial and might influence the study results or ability to continue to comply with trial procedures

### **6.4 Withdrawal from Study**

Participation in the study is strictly voluntary. Participants have the right to withdraw from the study at any time and for any reason, without penalty. The investigator or PATH may, at their discretion, withdraw a participant from continuing in the study if it is considered to be in the participant's best interest to do so, or if the participant is not willing or able to comply with the study requirements. The reason for withdrawal will be documented in source document and relevant case report form (CRF).

In the event of withdrawal from study, reasonable efforts should be made to conduct the following procedures:

- Review memory aid if still in use prior to withdrawal
- Update any ongoing AE/SAEs that remain ongoing at time of participant's last visit prior to withdrawal
- Query about AEs/SAEs and concomitant medications if the interval between the participant's last visit and the time of withdrawal is within the protocol defined reporting period
- Physical examination including vital signs
- Obtain any interim stool samples the participant may have collected for the study
- Collect venous blood samples for safety laboratory testing if withdrawal occurs before Day 8 Visit, and for immunological testing if withdrawal occurs before Day 57 Visit
- Update contact information

All participants who withdraw from the study following study vaccination and in whom cessation of vaccine virus shedding has not been confirmed, will be required to continue providing stool specimens for analysis and continue with requirements for mitigating the risk of fecal transmission until cessation of

shedding is confirmed. If a participant does not adhere to the required provision of stool specimens to enable confirmation of cessation of shedding, the investigator shall notify the relevant local health department.

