## 2.3 Study Endpoints

### 2.3.1 Primary Endpoints:

#### Safety

- Frequency of serious adverse events (SAEs) from Day 1 study vaccination through the end of the study

- Frequency of solicited adverse events (AEs) for 7 days (day of study vaccination and 6 following days) after each dose of study vaccine
- Frequency of unsolicited AEs for 28 days (day of study vaccination and 27 following days) after each dose of study vaccine [including clinically significant aberrant safety monitoring laboratory values on Day 8 reported as AEs]

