#### **6.2.4 Day 29 Visit, 28 (+2) days after the study vaccination – Clinic follow-up visit**

At the Day 29 Visit, the participant will return to the study clinic for the following procedures:

- Collect any pending stool samples from the participant
- Collect any new AEs since Day 8 Visit that have not already been captured and review any AEs that are currently ongoing
- Collect any new concomitant medications since Day 8 Visit that have not already been captured and review any concomitant medications that are currently ongoing

- If the participant reports any intervening symptom or AE since the previous visit, perform a targeted physical examination, which is to include vital signs
- Any topics or new information considered by investigator to be important to continued informed consent to be shared with the participant
- Collect venous blood sample (approximately 10 mL) for neutralizing antibodies to type-specific polioviruses

For participants in Cohorts 1 or 3, who were randomized to receive only a single dose of study vaccine:

- Provide participant with instructions and supplies to collect stool specimens within the appropriate windows on study Days 36, 43, 50, and 57 prior to their next scheduled visit
- Provide participant clear guidance on appropriate hygienic measures and supplies to minimize contact and contamination during the stool collection process (e.g., collection kit, sanitizer, disinfectant, gloves) and minimize risk of transmission of vaccine virus to others. Ask participant to describe these measures ('teach back method') for hand washing and stool collection before leaving the clinic and correct any errors
- Provide participant information about storage and transport of stool specimens to the study site
- Schedule next study visit (Day 169 Visit), which will occur via telephone, and instruct participant to contact study staff for any symptoms of concern and ensure participant has appropriate contact details for the study team
- Inform participant that if cessation of vaccine virus shedding is not confirmed by Day 57 stool sample, they will be asked to continue with stool collections and the associated protocol restrictions until they are informed that cessation of shedding has been confirmed

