## 8.2 Reporting Period and Parameter

Safety events are reported from the time of signing the ICF through each participant's completion of the study 168 days after their Day 1 study vaccination. Specifically, solicited AEs will be collected for 7 days (day of study vaccination and 6 following days) after each dose of study vaccine. If a solicited AE started during the 7 days post-vaccination and continues beyond the 7 days, it will continue to be reported as a solicited AE. Unsolicited AEs will be collected for 28 days (day of study vaccination and 27 following days) after each dose of study vaccine. SAEs will be collected from Day 1 study vaccination through the end of the study (Day 169 Telephone visit).

Any untoward medical occurrence after signing the ICF but before receipt of study vaccine, although not to be reported as an AE, if it is assessed as related to participation in the study, must still be reported by email to PATH within 3 days of awareness.

Due to uncertainties around the COVID-19 pandemic and the potential for stay-at-home orders, if a subject is unable to come to the clinic for a visit, the scheduled and applicable safety assessments may be conducted by telephone.

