#### **8.5 Follow-up of Adverse Event**

All reported AEs should be followed until resolution or stabilization, or until the participant’s participation in the study ends. The investigator must ensure that any AEs that are ongoing at study completion have been appropriately referred to the local health care system for continuation of care. Participants who have an ongoing study vaccine related SAE at study completion or at discontinuation from the study will be followed by the investigator until the event is resolved or determined to be irreversible, chronic, or stable by the investigator.

The outcome of adverse events will be assessed at the time of last observation as per the following categories:

- Recovered/resolved without sequelae
- Recovered/resolved with sequelae
- Recovering/resolving
- Not recovered/not resolved
- Fatal
- Unknown. The outcome of the AE is not known

Due to uncertainties around the COVID-19 pandemic, if a subject has a reportable adverse event that meets the clinical criteria of the current CDC case definition of COVID-19, the investigator will ensure that the subject will undergo standard of care diagnostic testing and if needed, a quarantine period for SARS-CoV-2.

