## 8.7 Reporting of SAEs

PATH has designated Emmes with authority to coordinate SAE reporting activities. All SAEs which occur during the study, whether considered to be associated with the study vaccine or not, must be reported within 24 hours of the site becoming aware of the event to the Emmes Medical Monitor by one of the mechanisms provided (e.g., electronic data capture [EDC] system, email, or fax). Contact details and instructions for submitting SAEs will be provided in a handout located in the Investigator Site File. If the SAE is fatal or life-threatening, the study medical monitor shall be informed immediately by email.

The investigator should not wait for additional information to fully document the event before notifying Emmes. When additional information becomes available, follow-up submissions will be submitted. The initial SAE form should be completed with all information known at the time and should include minimal elements for initial assessment:

- Name and contact of the investigator submitting the SAE report
- Participant ID number
- Date participant received study vaccine

- Description of the SAE and date of event onset
- Investigator's preliminary assessment of severity and causality

When applicable, hospital case records and autopsy reports should be obtained (without name or personal identifiers).

The investigator is also responsible for reporting all SAEs to their IRB/IEC in accordance with institutional policy and adequate documentation of this reporting must be provided to Emmes.

Reporting procedures for all SAEs will be followed as per FDA regulatory guidelines. The study Safety Management Plan (SMP) will contain all the details of safety and regulatory reporting. Emmes is responsible for safety reporting to the FDA within the following time periods:

- Serious and unexpected suspected adverse reaction within 15 days of awareness
- Fatal or life-threatening suspected adverse reaction within 7 days of awareness

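### After a withdrawal by the investigator or sponsor under section 6.4, new SAEs are captured only passively, although the primary SAE endpoint runs to the Day 169 call

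*Protocol*

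**What the plan says.** Section 2.3.1 makes this a primary endpoint: "Frequency of serious adverse events (SAEs) from Day 1 study vaccination through the end of the study". Section 8.2 places the end of SAE collection at the Day 169 telephone visit.

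Section 6.4 states that the investigator or sponsor "may, at their discretion, withdraw a participant from continuing in the study if it is considered to be in the participant's best interest", with unwillingness or inability to comply as a second ground. Reasonable efforts are then made to complete a list of exit procedures. The item aimed at new events is "Query about AEs/SAEs and concomitant medications if the interval between the participant's last visit and the time of withdrawal" falls within the reporting period. The list also covers an update of ongoing AEs and SAEs, a physical examination with vital signs, bloods where they are still due, and updated contact details. After exit, stool collection and transmission precautions continue until shedding has stopped.

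Section 8.5 adds one exception: "Participants who have an ongoing study vaccine related SAE at study completion or at discontinuation from the study will be followed by the investigator". That follow-up lasts to resolution, or to a judgement that the event is irreversible, chronic or stable. Section 8.7 says that any SAE "must be reported within 24 hours of the site becoming aware of the event", and section 13.8 has participants told to contact staff about illness during the study.

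For cohorts 1 and 3 the last step at Day 29 is "Schedule next study visit (Day 169 Visit), which will occur via telephone" (section 6.2.4). At that call staff are to "Collect any new SAEs reported since previous Visit that have not already been captured and review SAEs that are currently ongoing" (section 6.2.7).

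**The concern.** Stopping vaccine or burdensome procedures is one decision, and stopping the search for SAEs is another. Section 6.4 lets the investigator or sponsor make both at once, with no need for the participant to have withdrawn consent. In cohorts 1 and 3 the Day 169 call is the only scheduled SAE contact after Day 29. In cohorts 2 and 4 it is the only one after Day 57. Omitting that one call removes all active SAE collection for the rest of the window.

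A withdrawal in the participant's best interest may well be related to health. Section 11.5.9 nevertheless starts from data missing completely at random. The SAP may add methods for missing-data patterns, but no analysis recovers an event that nobody asked about. This is a first-in-human trial whose safety results are to support testing in young children and infants (section 1), and at its group sizes a single SAE changes the reported interval noticeably.

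**Working it through.** **Provisions side by side**

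| Situation | Section | Safety follow-up afterwards |
|---|---|---|
| Participant declines vaccine or procedures | 6.3 | Encouraged to complete it |
| Emergency unblinding | 6.7 | Stays in the study, protocol follow-up continues |
| Pregnancy | 6.8 | Encouraged to complete remaining visits |
| Study pause | 9.3 | Vaccinated participants still followed |
| Withdrawal by investigator or sponsor | 6.4 | Exit procedures, then stool collection; 8.5 only for a related SAE already ongoing |

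Only the last row ends active SAE collection by a staff or sponsor decision. Section 6.3 sends many safety-driven cases to a vaccination stop. That has no practical effect after the last dose, which is Day 1 in cohorts 1 and 3 and Day 29 in cohorts 2 and 4.

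**Share of the SAE window without active collection**

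The window from Day 1 to Day 169 is 168 days. For a withdrawal at Day w the share is (169 − w)/168:

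- Day 8: 161/168 = 96%
- Day 29: 140/168 = 83%
- Day 57: 112/168 = 67%

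**The plan's own safety figure**

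Section 11.3 gives 4.2% as the lowest rate with 95% probability of at least one event at n = 70. This reproduces: 1 − 0.05^(1/70) = 4.19%. The figure n = 70 is the two nOPV groups of one type at maximum enrolment (20 + 50).

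**Effect on detection**

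The protocol states neither a withdrawal rate nor an SAE risk, so both are assumed here. Assume k participants withdrawn at Day 29, a constant hazard equal to everyone else's, and no passive capture of later events.

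- Cumulative hazard per participant: h = −ln(0.05)/70 = 0.04280
- Detection = 1 − exp(−(70h − k·h·140/168)) = 1 − 0.05·exp(0.03566k)
- k = 0: 95.00%; k = 1: 94.82%; k = 2: 94.63%; k = 3: 94.44%

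With three withdrawals at Day 8 the share is 161/168, so detection is 1 − 0.05·exp(3 × 0.04280 × 0.9583) = 94.3%. The Day 29 figures are therefore not a bound.

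**Chance that at least one SAE begins after exit**

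This is 1 − exp(−k·h·140/168) with h = −ln(1 − p), where p is the SAE risk over the full window:

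| p | k = 1 | k = 3 |
|---|---|---|
| 1% (assumed) | 0.8% | 2.5% |
| 2% (assumed) | 1.7% | 4.9% |
| 4.19% (detection threshold at n = 70) | 3.5% | 10.1% |

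The last row uses the table's detection threshold. It is not an expected SAE risk in screened healthy adults.

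**What one event is worth**

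In the section 11.3 table the upper 95% limit moves from 21.8% to 31.9% at n = 15, and from 7.1% to 10.6% at n = 50, when one event is observed instead of none.

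**The case against.** The discretion in 6.4 is ordinary, and nothing in the protocol is contradicted. Section 6.3 already directs safety concerns, intercurrent illness and repeated non-compliance to a vaccination stop, which leaves 6.4 as the residual route. After Day 29, cohorts 1 and 3 have only stool collection and one telephone call left, so it is hard to see why ending participation then would serve anyone's interest. Those unwilling to comply may miss the call anyway. Section 1.5.1 reports that no AE led to withdrawal in the nOPV2-c1 trials. Reasons for withdrawal are recorded, and dropout is reported with a CONSORT diagram (section 11.5.4). The Safety Management Plan, which is not available here, may say more.

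Most of this stands as an argument about size: few such withdrawals are likely. It does not close the gap. No provision says whether 6.3 or 6.4 governs when the grounds overlap, and a light remaining schedule is equally a reason to keep the call. Reporting the dropout shows that follow-up ended, but not what happened afterwards.

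Three stronger readings do not hold:

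- **A reader might infer that a withdrawn participant leaves with nothing but a query, and that later SAEs are simply lost.** The exit procedures are wider than that, stool collection can keep the site in contact for a time, section 8.5 covers related SAEs ongoing at exit, and sections 8.7 and 13.8 leave passive reporting open.
- **A reader might take the figures above as upper bounds on missed events.** They assume average risk and Day 29. Earlier or health-related withdrawals would carry more risk, while passive reports would recover some events.
- **A reader might conclude that SAE rates will use a wrong denominator.** How partial follow-up enters the denominators can be settled in the SAP and is not at issue here.

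**Conclusion.** The point holds as a small gap in data collection that is cheap to close. As written, 6.4 allows the investigator or sponsor to end active collection for a primary safety endpoint for reasons that may be related to health. New SAEs then depend on someone telling the site.

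For each person withdrawn, 83% of the window is affected at Day 29 and 67% at Day 57. Across the trial the expected effect is small: under average risk, one to three Day 29 withdrawals lower detection at n = 70 by about 0.2 to 0.6 percentage points. That size rests on an assumed number of withdrawals, a constant and equal hazard, and no passive capture. Selective loss of a health-related event is the more serious possibility, and the protocol gives nothing from which to estimate it.

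**What to change.** Keep the discretion to stop vaccination and burdensome procedures. Add one sentence to section 6.4, for example:

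*Participants withdrawn by the investigator or sponsor after vaccination remain in SAE follow-up, including the scheduled Day 169 telephone call, unless they withdraw consent or refuse.*

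The cost is that sentence and a call already in the schedule. Contact details are already updated at withdrawal, and 6.4 already requires stool samples after exit, so later contact is foreseen. Sample size and analyses do not change. The downside is that staff must still try to reach some non-compliant participants. Some will refuse or be unreachable, so the gain is partial.
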